6.2.3 Blinding

The principal investigators, the statistician, and members of the data collection team will remain blinded to intervention assignment throughout the duration of the study. They will be given the identifying codes only at the end of the study when it is necessary to interpret the results. The un-blinded study coordinator, who is responsible for scheduling testing and treatment sessions, will greet participants and

escort them to the testing lab; however, the study coordinator will not participate in the assessments of clinical outcomes or testing.

6.2.4 Follow-up Visits

Treatment visit assessments for each visit 2-19 include the following:

- Numeric Pain Rating Scales 7-day & 24-hour
- Medication Log
- Adverse Events Log
- Numeric Pain Rating Scale – Right Now
- Standardized Reaching Paradigm (Pain & Harm Expectancy, Lumbar Spine Flexion)

Assessments at first post-treatment follow-up visit, Visit 20, include:

- Numeric Pain Rating Scales 7-day & 24-hour
- Roland-Morris Disability Questionnaire
- Medication Log
- Adverse Events Log
- Numeric Pain Rating Scale – Right Now
- Standardized Reaching Paradigm (Pain & Harm Expectancy, Lumbar Spine Flexion)
- Tampa Scale for Kinesiophobia
- Center for Epidemiologic Studies – Depression
- Pain Catastrophizing Scale
- Pain Resilience Scale
- Pain Self Efficacy Questionnaire
- Brief Pain Inventory – Short Form
- PROMIS-Anxiety
- PROMIS-Depression
- PROMIS-Positive Affect
- PROMIS-Meaning and Purpose Scale
- Life Fulfillment Scale
- Profile of Mood States
- Real World Activity Monitoring
- Treatment Evaluation Inventory – Short Form
- Patient Global Impression of Change

Assessments at post-treatment follow-up visits 21-24 include:

- Numeric Pain Rating Scales 7-day & 24-hour
- Roland-Morris Disability Questionnaire
- Medication Log
- Adverse Events Log
- Numeric Pain Rating Scale – Right Now
- Standardized Reaching Paradigm (Pain & Harm Expectancy, Lumbar Spine Flexion)
- Tampa Scale for Kinesiophobia
- Center for Epidemiologic Studies – Depression
- Pain Catastrophizing Scale
- Pain Resilience Scale

- Pain Self Efficacy Questionnaire
- Brief Pain Inventory – Short Form
- PROMIS-Anxiety
- PROMIS-Depression
- PROMIS-Positive Affect
- PROMIS-Meaning and Purpose Scale
- Life Fulfillment Scale
- Profile of Mood States
- Real World Activity Monitoring
- Treatment Evaluation Inventory – Short Form

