6. STUDY PROCEDURES

6.1 Schedule of Evaluations

Assessment	Prescreen	Screen Visit 0	Enrollment & Baseline Visit 1	Treatment Visits 2-19	Post-Treatment Assessments Visit 20	Post-Treatment Assessments Visits 21-24
Numeric Pain Rating Scales 7-day & 24-hour	X	X	X	X*	X	X
Roland-Morris Disability Questionnaire	X	X	X		X	X
Fear Question	X	X				
Medical History - Back Pain	X	X				
Medication Log		X	X	X	X	X
Informed Consent Form		X				
Inclusion/Exclusion Criteria		X				
Enrollment/Randomization		X				
Medical History		X				
Physical Exam Form		X				
Adverse Events			X	X	X	X
Numeric Pain Rating Scale - Right Now			X	X	X	X
Standardized Reaching Paradigm • Pain & Harm Expectancy • Lumbar Spine Flexion			X	X*	X	X
Tampa Scale for Kinesiophobia			X		X	X
Center for Epidemiologic Studies - Depression			X		X	X
Pain Catastrophizing Scale			X		X	X
Pain Resilience Scale			X		X	X
Pain Self Efficacy Questionnaire			X		X	X
Brief Pain Inventory - Short Form			X		X	X
PROMIS-Anxiety			X		X	X
PROMIS-Depression			X		X	X
PROMIS-Positive Affect			X		X	X
PROMIS – Meaning and Purpose Scale			X		X	X
Life Fulfillment Scale			X		X	X
Profile of Mood States			X		X	X
Real World Activity Monitoring			X		X	X
Treatment Evaluation Inventory - Short Form			X		X	
Patient Global Impression of Change					X	X

*assessed at the first visit of each week

Note: Prescreening, Visit 0 screening, Visit 1 baseline, and Visit 2 first intervention can all occur on the same day.

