Real World Activity Monitoring: Following pre-treatment baseline and each of the post-treatment assessments, the participant will be given an activity monitor to wear on the non-dominant wrist for 1-week and returned to the laboratory by pre-paid postage. The total number of steps/day will be the primary dependent variable to determine the effects virtual dodgeball on activity levels measured in a natural environment (Aim 3). We will also examine ancillary outcomes of physical activity intensity by examining step cadence and using standard thresholds to aggregate data into sedentary, light, moderate, and vigorous activity.⁵⁹

Treatment Evaluation Inventory – Short Form: To assess participant acceptance of the intervention, we will administer a modified version of the Treatment Evaluation Inventory, Short Form⁶⁰ at Visit 1 and again at Visit 20 (i.e., 1-week follow-up).

Patient Global Impression of Change: This scale is used to quantify a participant's perception of their level of positive, negative, or no change as a function of participating in the intervention. It will be included among our additional analyses.

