6.2.5 Completion/Final Evaluation

Assessments to be performed at the participant's final visit include:

- Numeric Pain Rating Scales 7-day & 24-hour
- Roland-Morris Disability Questionnaire
- Medication Log
- Adverse Events Log
- Numeric Pain Rating Scale – Right Now
- Standardized Reaching Paradigm (Pain & Harm Expectancy, Lumbar Spine Flexion)
- Tampa Scale for Kinesiophobia
- Center for Epidemiologic Studies – Depression
- Pain Catastrophizing Scale
- Pain Resilience Scale
- Pain Self Efficacy Questionnaire
- Brief Pain Inventory – Short Form
- PROMIS-Anxiety
- PROMIS-Depression
- PROMIS-Positive Affect
- PROMIS-Meaning and Purpose Scale
- Life Fulfillment Scale
- Profile of Mood States
- Real World Activity Monitoring
- Patient Global Impression of Change

All assessments will be performed for participants who discontinue study intervention early.

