9.6 Data Analyses

We will analyze all outcome variables (pain, disability, pain/harm expectancy, and lumbar flexion) using linear mixed-effects (LME) models with treatment (Experimental, Control) as a between-subject fixed effect and time (pre-treatment, 1, 6, 12, 24, and 48 weeks) as a within-subject fixed effect. Given the expected findings, both linear and quadratic time effects will be tested in every model. We will also include demographic covariates (e.g., age, BMI) and potential confounders (e.g., radiating versus non radiating pain) as well as sex stratification in the LME models. Any variables that differ at baseline will be included in the statistical models as potential confounders.

Intention-to-treat analyses are commonly conducted to analyze randomized clinical trial data in the presence of missing values. While various imputation strategies have been proposed to estimate missing data, such as last observation carried forward, use of LME models to analyze longitudinal data renders these strategies largely unnecessary. We will also conduct equivalent per-protocol analyses that will include only successfully adhered participants (i.e., attending $\geq 70\%$ of gaming sessions).

Aim 1. Examine immediate clinical outcomes as a function of treatment. Relative to

the control group, participants in the experimental group will show greater reductions in pain and disability at post-treatment relative to pre-treatment baseline (Hypothesis 1).

To test Hypothesis 1, we will examine the Treatment by Time (baseline-post treatment) interaction in a LME model: a greater reduction in pain and disability in the experimental group than in the control group.

Aim 2. Examine potential mechanisms of pre- to post-treatment changes in clinical outcomes. Participants in the experimental group will exhibit greater pre- to post-treatment decreases in pain/harm expectancy and increases in lumbar flexion as compared to the control group (Hypothesis 2.1). Decreases in pain/harm expectancy and increases in lumbar flexion will be positively related to pre- to post-treatment reductions in pain and disability (Hypothesis 2.2).

Aim 3. Examine maintenance of treatment gains at 1-, 6-, 12-, 24-, and 48-weeks post-treatment. Relative to the control group, participants in the experimental group will continue to show lower levels of pain and disability at each time point as well as increased activity in their natural environment (Hypothesis 3).

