To address aims 2 & 3 we will build and test linear mixed-effects models for each of the outcome variables. For hypotheses 2.1 and 3, pain, disability, pain/harm expectancy, and lumbar flexion will be the outcome variables, while time (linear and quadratic), treatment group, and the interactions of time and treatment group will be the primary predictor variables. For hypothesis 2.2, pain/harm expectancy and lumbar flexion will serve as the outcome variables, while time (linear and quadratic), treatment group, the time-by-group interactions, pain, and disability will be predictor variables. For hypothesis 3, planned comparisons will be conducted to compare the control and experimental groups at each time period for pain, disability, and activity levels in the natural environment. As noted above, covariates will be added to analyses as needed. The significance level for every omnibus test will be set to 0.05, while Holms procedure will be used to control familywise type-I error rate for post-tests at .05.

Checking Assumptions: Assumptions of LME models will be checked by conducting analyses of model residuals. Violations of normality will be addressed by transforming the data, while outliers or influential cases will be handled by conducting sensitivity analyses. In contrast to the standard repeated measures analyses of variance, with their rigid assumptions about the error covariance structure, LME models permit numerous alternative error covariance structures. This allows for modeling of data that exhibit both heteroscedasticity and autocorrelation, which is likely to characterize the data collected for this study.

Additional Analyses: We will use the same analytic framework to analyze additional measures of core outcome domains, including emotional functioning (e.g., CES-D, POMS-2, PROMIS measures), pain vulnerability (TSK, PCS), pain resilience (PRS, PSEQ), and patient global impression of change (PGIC).

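### The Section 6.2.4 list for visits 21-24 omits the Patient Global Impression of Change and includes the Treatment Evaluation Inventory, the reverse of the schedule table, Section 6.2 and the final-visit list

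*Combined protocol and SAP*

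**What the plan says.** Four places set the timing of the two questionnaires.

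- **Section 6.1, schedule table.** Visit 20 and Visits 21-24 have separate columns. The PGIC row ("Patient Global Impression of Change X X") is marked in those two columns and nowhere earlier. The TEI-SF row ("Treatment Evaluation Inventory - Short Form X X") is marked at Visit 1 and Visit 20.
- **Section 6.2, instrument descriptions.** TEI-SF measures acceptance of the intervention and is given "at Visit 1 and again at Visit 20 (i.e., 1-week follow-up"). PGIC is described as the participant's perception of change from taking part, and no visits are named.
- **Section 6.2.4, follow-up lists.** The Visit 20 list contains both instruments. The next list, headed "Assessments at post-treatment follow-up visits 21-24 include", contains TEI-SF and not PGIC.
- **Section 6.2.5, final evaluation.** The list headed "Assessments to be performed at the participant's final visit include" contains PGIC and not TEI-SF.

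On analysis, Section 9.6 states "We will use the same analytic framework to analyze additional measures of core outcome domains" and names PGIC among those measures. The framework is a linear mixed-effects model with treatment as a between-subject effect and "time (pre-treatment, 1, 6, 12, 24, and 48 weeks) as a within-subject fixed effect". TEI-SF is not named in Section 9.6.

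**The concern.** Visit packets and electronic forms are often built from the visit-by-visit lists, and nothing in the document says whether the lists or the table governs. If Sections 6.2.4 and 6.2.5 are followed literally, the only global rating of change made by participants is missed at three of the visits that address maintenance of gains. A rating that is not taken at its visit cannot be recovered later. In exchange, participants complete an acceptability scale at visits for which the plan gives it no purpose.

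A smaller gap concerns the model. PGIC is itself a rating of change and so has no pre-treatment value, yet it is sent to a framework whose first time level is pre-treatment. No sentence says how that level is handled for PGIC, or which contrast will be reported.

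**Working it through.** No sample size, power or alpha figure is involved. The check sets the lists side by side.

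**Step 1: item counts at Visits 21-24.**

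- The schedule table marks 20 assessments in the Visits 21-24 column.
- The Section 6.2.4 list for the same visits has 20 items.
- Nineteen are common to both. The one left over is PGIC in the table and TEI-SF in the list.

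The mismatch is therefore a one-for-one swap. The list is complete, so it is not a truncation.

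**Step 2: which source stands alone.**

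| Source | PGIC after Visit 20 | TEI-SF after Visit 20 |
|---|---|---|
| 6.1 schedule table | Yes, Visits 21-24 | No |
| 6.2 descriptions | Timing not given | No (Visits 1 and 20) |
| 6.2.4 list, Visits 21-24 | No | Yes |
| 6.2.5 list, final visit | Yes | No |

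Section 6.2.4 is the only source that puts TEI-SF after Visit 20, and the only one that leaves PGIC out. For a participant who completes follow-up, the final visit is Visit 24, so the two text lists also contradict each other at that visit.

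**Step 3: PGIC occasions under each reading.**

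- Table: Visits 20, 21, 22, 23 and 24 (weeks 1, 6, 12, 24 and 48) = 5.
- Section 6.2.4 lists alone: Visit 20 = 1.
- Sections 6.2.4 and 6.2.5 together: Visits 20 and 24 = 2.
- Shortfall with both text lists followed: 5 − 2 = 3 occasions, at Visits 21, 22 and 23 (weeks 6, 12 and 24).

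**Step 4: PGIC against the model in Section 9.6.** The time factor has 6 levels: pre-treatment plus 5 follow-ups. PGIC is absent from the Visit 1 column of the table and from the Visit 1 list in Section 6.2.2, so it can fill at most 6 − 1 = 5 levels. A contrast from baseline to a later visit does not exist for it. The treatment term, and the arm difference at each post-treatment visit, can be estimated from those 5 levels.

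**The case against.** The best defence is that the intended schedule is plain. The table and Section 6.2.5 both place PGIC after Visit 20, and together with Section 6.2 they all exclude TEI-SF there. Section 6.2.4 looks like a copying slip, in which the wrong one of the last two items was dropped when the Visit 20 list was shortened. Staff who work from the table would lose nothing. This stands in part: it settles what the correction should be, and it makes the loss conditional. It does not remove the contradiction, because no rule says which source prevails.

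A second defence is that PGIC carries little weight in the trial. It is neither a primary nor a secondary outcome in Section 9.5, and Hypothesis 3 covers pain, disability and activity. This stands.

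On the modelling gap, a reader might infer that Section 9.6 cannot test an arm difference in PGIC at all, because a constant benefit would give a null treatment-by-time interaction. The documents do not support that reading. The baseline-to-post interaction is stated as the test for Hypothesis 1, which concerns pain and disability. The general framework has treatment as an effect in its own right, and Section 9.6 plans arm comparisons at each time period under Hypothesis 3. A mixed model on Visits 20-24 within that framework can show a constant arm difference. What remains is narrower: the per-visit comparisons name pain, disability and activity but not PGIC, and the use of post-treatment visits only is not stated.

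**Conclusion.** The Section 6.2.4 list for Visits 21-24 is wrong as written and must be reconciled with Sections 6.1, 6.2 and 6.2.5. The size is 3 of 5 planned PGIC occasions. That rests on two assumptions: that staff follow the text lists rather than the table, and that the final visit is Visit 24.

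A reader might turn this into a count of lost ratings, such as 3 × 209 = 627. The documents do not support that figure. In Section 9.2, 209 is the minimum sample from the power calculation, not a forecast of attendance at Visits 21-23, and the loss itself is conditional.

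The analysis of PGIC needs a clarification and is not invalid. The co-primary outcomes, Hypothesis 3 and the sample size are untouched. The correction is worth making because it changes which data are collected.

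**What to change.** 1. **Section 6.2.4.** In the list for Visits 21-24, replace TEI-SF with PGIC. The list then agrees with the table in 6.1, the TEI-SF timing in 6.2 and the final-visit list in 6.2.5. Check that visit packets and electronic forms match.
2. **Section 9.6, minor clarification.** Add one sentence: PGIC has no baseline by design, is modelled on post-treatment visits only (Visits 20-24), and the reported contrast is the arm difference at each visit.

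The cost is wording in two sections. One questionnaire replaces another at four visits, so the number of assessments per visit stays at 20. No change to the sample size or the primary analysis is needed.

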6.2.5 Completion/Final Evaluation

Assessments to be performed at the participant's final visit include:

- Numeric Pain Rating Scales 7-day & 24-hour
- Roland-Morris Disability Questionnaire
- Medication Log
- Adverse Events Log
- Numeric Pain Rating Scale – Right Now
- Standardized Reaching Paradigm (Pain & Harm Expectancy, Lumbar Spine Flexion)
- Tampa Scale for Kinesiophobia
- Center for Epidemiologic Studies – Depression
- Pain Catastrophizing Scale
- Pain Resilience Scale
- Pain Self Efficacy Questionnaire
- Brief Pain Inventory – Short Form
- PROMIS-Anxiety
- PROMIS-Depression
- PROMIS-Positive Affect
- PROMIS-Meaning and Purpose Scale
- Life Fulfillment Scale
- Profile of Mood States
- Real World Activity Monitoring
- Patient Global Impression of Change

All assessments will be performed for participants who discontinue study intervention early.

6.2.6 Reasons for Early Termination

A subject would be discontinued from the study intervention if a medical condition develops that precludes the continuation of the treatment intervention. For participants who discontinue The VIGOR Study prior to completing all scheduled treatment sessions (regardless of the reason), we will make every attempt to obtain the outcome measurements. If the study participant is unwilling or unable to undergo the laboratory-based tests (e.g., difficulty tolerating the protocol, experienced an adverse event to a lab test) we will still attempt to obtain the clinical outcome

measures. In instances where an adverse event does occur, we will follow-up with participants until the event is resolved or until the IRB deems it unnecessary to continue to follow the participant.

If the participant complains of any sudden onset of muscle or joint pain, the current session will be terminated, and the Principal Investigator will be contacted to complete an assessment. If he is unavailable, one of the other clinicians on the study team will be contacted to provide a clinical assessment of the participant. They will then consult with the PI to assess if the participant should continue to stay on protocol. If an exclusion criterion is identified from the presenting signs and symptoms, the participant will then be withdrawn from the study. If the presenting signs and symptoms do not meet the exclusion criteria, the participant will be invited to return for their next scheduled visit when the sudden onset of symptoms has abated. Upon return, the PI or a clinician on the study team will again assess the participant and make a clinical judgement about their fitness to continue with the intervention. However, if the participant has a second episode of sudden onset of joint or muscle pain, they will be immediately withdrawn from the study.

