Our co-primary outcome variables will be change in pain and change in disability from baseline to 1-week post-treatment (Aim 1). We will also examine changes in expectations of pain/harm and lumbar flexion as potential mechanisms of change in pain and disability (Aim 2). Aim 3 will examine maintenance of treatment gains at 1-, 6-, 12-, 24-, and 48-weeks post-treatment, additional measures of emotional functioning, pain vulnerability, and pain resilience, and real-world activity monitoring

[figure not shown]
(See Recruitment and Pre-Screening – Figure1).

Figure 1

Study Title

VIGOR - Virtual Immersive Gaming to Optimize Recovery in Low Back Pain

Objectives

The co-primary clinical outcomes are changes in pain and disability. Secondary objectives are to examine potential mechanisms of pre- to post-treatment changes in clinical outcomes and maintenance of treatment gains.

Design and Outcomes

VIGOR is a Phase II, double-blind, randomized, placebo-controlled trial to test the efficacy and safety of a novel, immersive, virtual reality intervention on outcomes of pain, disability, pain/harm expectancy, and lumbar flexion in individuals aged 18-60 years of age with chronic low back pain.

Individuals with chronic low back pain will be randomly assigned to play one of two versions of the virtual reality game suite for 9-weeks. In the experimental group, gameplay will promote progressive increases in lumbar flexion. The control group will play the same immersive video games, but the parameters will be modified such that

only small excursions of lumbar flexion are needed to successfully complete gameplay. The co-primary clinical outcomes of changes in pain and disability will be assessed at 1-, 6-, 12-, 24-, and 48-weeks post-treatment. Additionally, individual differences in expected pain, expected harm, and lumbar flexion will be measured at pre-treatment baseline and at each of the follow-up intervals in the laboratory. Finally, participant activity in their natural environment will be monitored for 7 days following each follow-up laboratory visit using accelerometry.

Interventions and Duration

Participants will complete 18 intervention visits over 9 weeks with the number of sessions tapered across weeks (i.e., 3 sessions/week in weeks 1-3, 2 sessions/week in weeks 4-6, and 1 session/week in weeks 7-9).

Sample Size and Population

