Pain & Harm Expectancy: Consistent with our prior work,^{20, 46, 47, 53} expectations of pain and harm will be measured during standardized reaches performed at pre-treatment baseline, the first visit of each week of interventions, and post-treatment. Specifically, for each target height, prior to the first reaching trial, participants will be asked to rate the level of “expected pain” and “expected harm” using a visual analog scale displayed through the head mounted display (e.g., HTC Vive). The scale will consist of a 10 cm horizontal line with no numbers, marks, or descriptive vocabulary along its length. For expected pain ratings, the scale will be anchored with the descriptors “No pain” and “Worst pain imaginable”, respectively, at each end of the line. For expected harm, the scale will be anchored with “Not at all concerned” and “Extremely concerned” regarding potential harm to the back during task performance. Participants will indicate their response by moving a virtual sliding scale. Expectations of pain/harm will be used as dependent variables in Aim 2.

Tampa Scale for Kinesiophobia: This is used to assess candidate’s level of fear of movement due to perceived risk for back injury or re-injury. It is one of two pain vulnerability measures assessed in the study and is included among our additional analyses.

Center for Epidemiologic Studies – Depression: We will administer the Center for Epidemiological Studies-Depression (CES-D) scale⁵⁴ to assess symptoms of depression that often accompany chronic pain. The CES-D is included among our additional analyses as a measure of emotional functioning.

Pain Catastrophizing Scale: This survey is used to identify characteristics of rumination, magnification, and helplessness in the face of ongoing or intense pain. It is one of two pain vulnerability measures assessed in the study and is included among our additional analyses.

Pain Resilience Scale: This survey is used to measure behavioral perseverance as well as cognitive and affective positivity in the face of intense or prolonged pain. It is one of two pain resilience measures assessed in the study and is included among our additional analyses.

Pain Self Efficacy Questionnaire: This survey is used to measure the respondent’s confidence in their ability to carry out daily and enjoy daily activities despite pain. It is

one of two pain resilience measures assessed in the study and is included among our additional analyses.

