9.5.2 Secondary Outcomes

Secondary outcomes include expected pain, expected harm, and lumbar flexion during standardized reaching, which will be measured at pre-treatment baseline (visit 1), at the beginning of each week during treatment (visits 2, 5, 8, 11, 13, 15, 17, 18, 19), and at 1-, 6-, 12-, 24-, and 48-weeks post-treatment (i.e., visits 20-24).

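### Early stoppers who do not do the reaching test lose all three laboratory outcomes at that visit, and the Hypothesis 2.1 models make no stated use of the pain and disability scores still collected

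*Combined protocol and SAP*

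**What the plan says.** **Collection after early stopping.** Sections 6.2.6 and 8 promise every attempt to obtain outcomes. They then give a fallback: if a participant is unwilling or "unable to undergo the laboratory-based tests (e.g., difficulty tolerating the protocol, experienced an adverse event to a lab test"), the clinical outcome measures are still sought. Section 6.2.5 lists the reaching paradigm among the final assessments and states: "All assessments will be performed for participants who discontinue study intervention early".

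**What depends on the reaching test.** Section 9.5.2: "Secondary outcomes include expected pain, expected harm, and lumbar flexion during standardized reaching". The Précis (Design and Outcomes) has these measured "expected pain, expected harm, and lumbar flexion will be measured at pre-treatment baseline and at each of the follow-up intervals in the laboratory". In Section 6.2 the expectancy ratings come before movement: for each target height, "prior to the first reaching trial, participants will be asked to rate the level of" expected pain and expected harm, on a scale shown in the headset. Section 9.5.2 also schedules these measures "at the beginning of each week during treatment (visits 2, 5, 8, 11, 13, 15, 17, 18, 19").

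**Analysis.** Section 9.6 fits one mixed model per outcome, with time levels at baseline and 1, 6, 12, 24 and 48 weeks. For Hypothesis 2.1 the predictors are time, group, their interactions and covariates as needed. Pain and disability are named as predictors only for Hypothesis 2.2. Section 9.3 uses LOCF if data are judged MCAR, maximum likelihood if MAR, and multiple imputation if MNAR, without listing imputation variables. Section 9.6 says of imputation strategies that "use of LME models to analyze longitudinal data renders these strategies largely unnecessary".

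**The concern.** Hypothesis 2.1 is the mechanism test: does the experimental game lower pain and harm expectancy and raise flexion more than the control game? At a visit where the fallback applies, all three outcomes of that test are absent. The reasons the plan foresees could well go with high expectancy or low flexion.

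A likelihood mixed model for a single outcome is valid if missingness depends only on what that model conditions on. Here it would condition on the outcome's own baseline and follow-up values and any covariates. It would not condition on the pain and RMDQ scores collected at the same visit, nor on the weekly on-treatment laboratory values, which are outside the listed time levels.

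If people with worse values drop out of the laboratory data more often in one arm, that arm looks better than it is. Section 9.3 offers a richer method only after MNAR has been found, and observed data cannot separate MAR from MNAR. Multiple imputation in its usual form also assumes MAR, so naming it does not by itself address MNAR.

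**Working it through.** **1. The plan's own figure.** Section 9.2 gives δ = 0.45, residual variance 1, slope variance 0.30, power 0.80 and α = 0.05. I assume two-sided testing, 1:1 allocation and five equally spaced waves; the wave count is inferred.
- R = 0.30/(0.30 + 1/10) = 0.75
- N = 4(1.960 + 0.842)²/(0.45² × 0.75) ≈ 207; the noncentral F gives 209, as stated. Four waves give 261 and six give 187.
- 209 × 1.10 = 229.9, so 230.

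The 10% is total attrition to 48 weeks across both arms. There is no separate figure for people who stay in contact but miss the laboratory test. Below, 0.45 serves only as a yardstick.

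**2. Bias when refusal depends on the unseen value.** Let Y0 and Y1 be the standardised outcome at baseline and 1 week (higher is worse), with correlation r. In each arm the top fraction m on a score correlated c with Y1 refuse. Put q = Φ⁻¹(1−m), λ = φ(q)/(1−m), k = qλ + λ².
- Slope among those observed: β = r(1 − c²k)/(1 − c²r²k)
- Error in the arm's estimated 1-week mean: b(m) = −cλ(1 − rβ)
- Bias of the contrast: b(experimental) − b(control)

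Example with r = 0.5, c = 1:
- m = 10%: λ = 0.1950, k = 0.2879, β = 0.3837, b = −0.1950(1 − 0.1918) = −0.158
- m = 3%: λ = 0.0701, k = 0.1369, β = 0.4469, b = −0.0545
- Contrast: −0.158 + 0.0545 ≈ −0.103 SD, favouring the experimental arm

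Over r = 0.5-0.7 (Section 9.2 uses 0.7 for Aim 1) and c = 0.5-1.0:

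| Assumed refusal, experimental v control | Bias (SD) | Share of 0.45 | Favours |
|---|---|---|---|
| 5% v 3% | 0.010-0.031 | 2-7% | experimental |
| 10% v 5% | 0.023-0.072 | 5-16% | experimental |
| 10% v 3% | 0.033-0.103 | 7-23% | experimental |
| 15% v 5% | 0.045-0.141 | 10-31% | experimental |
| equal | 0 | 0 | neither |
| 5% v 10% | 0.023-0.072 | 5-16% | control |

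For scale, the standard error of the baseline-adjusted contrast at N = 209 is 2√((1−r²)/209): 0.099 at r = 0.7 and 0.120 at r = 0.5.

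**3. What the clinical scores can recover.** Take 15% v 5%, r = 0.7, a laboratory-clinical correlation of 0.3, 0.5 or 0.7 (assumed), and a refusal score equal to the driving variable plus noise of equal variance.

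| Refusal driven by | Own history only | With baseline and same-visit clinical score |
|---|---|---|
| clinical score | 0.018, 0.031, 0.044 | 0, 0, 0 |
| unseen laboratory value | 0.067, 0.067, 0.067 | 0.062, 0.052, 0.037 |

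In the second row the clinical score removes about 8%, 22% and 46% of the bias. A simulation with 400,000 records agrees with both rows to within about 0.005 SD.

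**The case against.** **Section 6.2.5 asks for every assessment, and the fallback applies only after every attempt.** True. This limits how many people are affected, but the sections still conflict. A reader might also infer that such participants give only pain and disability. Sections 6.2.6 and 8 do not define clinical outcome measures, and the questionnaires are not laboratory tests, so that goes too far.

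**The clinical data are used.** A reader might infer that the mixed models ignore them. They do not: pain and disability have their own models in the intention-to-treat set. The gap is confined to the laboratory-outcome models. In Hypothesis 2.2 pain and disability are predictors, but a visit with no laboratory outcome adds nothing to that likelihood.

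**Section 9.3 already provides multiple imputation.** Only on a finding of MNAR, and with no variables named.

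**Nothing shows that refusers are the most fearful.** Correct. Everyone enters with a Tampa score above 36. Intolerance could equally be nausea from the headset, a risk that Section 7 names. Section 7 also reports more than a decade of the reaching protocol without injury or sustained aggravation of pain.

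**The direction is open.** The larger flexion demand could raise refusal in the experimental arm. If treatment lowers harm expectancy as hypothesised, controls may refuse more. The documents do not support a claim that the bias favours the hypothesis.

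**Ratings before the reach are already planned.** The text does not say they would be discarded if the reach is declined, nor that they would be kept. They cannot be obtained from someone who does not attend or cannot wear the headset.

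**Conclusion.** The point holds in a limited form. The plan lets the three laboratory outcomes go missing together for potentially informative reasons, and the Hypothesis 2.1 models make no stated use of data already collected that could reduce the harm. Under the assumed unequal refusal of 10% v 3-5% or 15% v 5%, the bias is about 0.02-0.14 SD, or 5-31% of 0.45. It is about 0.01-0.03 SD at 5% v 3%, zero at equal rates, and reversed if controls refuse more. Most of these values are below one standard error. The refusal rates, correlations and mechanisms are all assumptions. In particular, the plan's 10% attrition should not be read as a refusal rate.

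Clinical auxiliaries remove the bias if refusal follows the clinical score. They remove less than half, and only 8-22% at correlations of 0.3-0.5, if it follows the unseen laboratory value. Imputation alone is therefore not enough. Importance is low to moderate: Hypothesis 2.1 is secondary and Hypothesis 1 is unaffected.

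**What to change.** Reconcile Section 6.2.5 with Sections 6.2.6 and 8, and define which measures count as clinical outcome measures. Then:

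1. For anyone who attends and accepts the headset, take and keep the expected-pain and expected-harm ratings even if the reach is declined. Flag them as not followed by a reach, and repeat the analysis without the flagged ratings.
2. Analyse Hypothesis 2.1 by a joint model or multiple imputation that includes arm, the outcome's history with the weekly on-treatment values, and same-visit NRS and RMDQ. Do not make this depend on a MAR or MNAR finding.
3. Add a delta-type MNAR sensitivity analysis, with the shift varied separately by arm.
4. Report missed laboratory tests and the reasons by arm and visit.

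The cost is protocol and SAP wording and a little more analysis, with no extra visit. The downside is that a rating not followed by a reach is partly hypothetical, hence the flag and the repeat analysis.
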